Objective 1: To evaluate the comparative effectiveness of patient-centered messages to enhance clinical trial participation, through a culturally tailored website, accessed using iPads, versus NYU's standard clinical trial participation website.

Hypothesis 1: Participants exposed to tailored messages about clinical trial literacy will exhibit greater likelihood in participating in clinical trials than those exposed to NYU's standard website.

Objective 2: To determine whether psychosocial factors (awareness of clinical trial, intrinsic motivation, health literacy, and self-efficacy) and medical factors (risk behavior, history of preventive behavior, and clinical diagnoses) mediate greater likelihood of participating in clinical trials among individuals exposed to the intervention.

[figure not shown]
Hypothesis 2: Greater likelihood of participating in clinical trials will be mediated by greater health literacy and self-efficacy independent of other individual-level factors (medical, knowledge, attitude/beliefs, and intrinsic motivation) and contextual-level factors (social support and socio-economic position).

Study Design

Objective 1: To evaluate the comparative effectiveness of a culturally and linguistically tailored clinical trial literacy website in increasing likelihood of participating in clinical trials. To achieve this objective, we will use a randomized group design, assessing the following patient-centered outcomes: willingness to enroll in clinical trials and behavioral intent as well as likelihood of referring others to enroll in such trials) before and after exposure to a culturally-tailored clinical trial literacy website. Health literacy will be measured both before and post exposure to tailored messages.

Participants will be randomized into two groups. The intervention group (n=50) will have access to culturally tailored website. Participants in the control group (n=50) will have access to NYU 's standard trial participation website.

Study Flowchart

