The ACTNOW conceptual framework was developed according to best practices and recommendations from the NIH Behavior Change Consortium (BCC) and was informed by CONSORT statements. Adherence to these recommendations ensures program implementation fidelity, thus enhancing the internal validity and generalizability of its findings. During the formative period, we will refine our strategies to ensure that all components are feasible and acceptable to potential participants and stakeholders (patients, leaders, and providers) comprising the Community Advisory Board. We will assemble and meet with a Community Advisory Board to seek endorsement of our implementation plan. We will also meet with leaders in representative communities to discuss plans for participant selection and enrollment to achieve our study objectives.

Study Duration

We estimate 4 months to assemble the Community Advisory Board, building consensus for project aims and materials, contracting all enrollment sites, and recruit participants. We estimate 3 months for initial meetings with stakeholders to discuss and endorse the implementation plan (Phase 1); 6 months for development and heuristic testing of the tailored website (Phase 2); 9 months for data collection and analysis in Phase 3, and 6 months for debriefing at the end of Year 2 and optimizing the website before dissemination (Phase 4).

II. SUBJECT IDENTIFICATION, RECRUITMENT AND CONSENT/ASSENT

1. Recruitment

We will use several recruitment strategies. First, we will utilize a recruitment funnel that we have developed from several studies (MetSo: IRB#S13-00897, Grant# NCT01946659; Multi-Site: IRB# v i13-00182, Grant# R01 HL095799-01A2; PEERS-ED: IRB# i14-01028, Grant# 5R01MD007716-02).

During the consent phase, all participants in these IRB approved studies are asked if they would like to be contacted for future studies. We have a recruitment pool of approximately 400 participants (who have completed studies) from which to draw upon who meet the eligibility criteria and who indicated that they would like to be contacted for future studies.

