Our collaborator from SUNY Downstate, [name], will conduct heuristic evaluation and cognitive walkthroughs of all web materials, and then perform standard formative usability testing onsite with 10 representative participants to ensure the site is well-suited to the needs of the intended community. These participants will be recruited from the existing pool of participants from previous RCT's mentioned above..

Participants will be contacted, and recruited for this portion of the study via telephone. Participants will be scheduled into time slots of approximately 40 minutes in duration. Participants will come to CHBC at their assigned timeslot, read and sign the consent form, and then begin the heuristic testing. She will ascertain whether health materials are acceptable and whether they capture daily experiences of potential patients whose lives vignettes intend to portray. She will recommend necessary changes based on log-file analysis that captures computer activity while the participant uses the website. In addition, [name] will ask participants several debriefing questions, such as their experience with the Internet, their willingness to use the resource in the future, and their overall user experience. This will ensure that messages are credible and understandable to the partner community.

Materials will also be presented to stakeholders in our Community Advisory Board for final approval. Once approved, materials will be available for use in the Intervention/Control Study.

Intervention/Control Study

Participants in the Intervention/Control study will be asked to come to the Center for Healthful Behavior Change for three discrete visits, including baseline, 1-month follow up, and 3-month follow up.

Baseline:

- I. Participants will be contacted from our prior IRB approved studies. Potential participants recruited through community locations and events like health fairs will also be contacted. All potential participants will be scheduled into an enrollment slot at which time they arrive at the CHBC ([name]) to fill out baseline surveys and receive study instructions.
- II. When participants arrive, they will be invited to go to either the intervention or control enrolment sessions. These groups will remain separate so as not to cross-contaminate instructions or materials.

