- III. Participants will receive the consent forms, and will be asked to read the documents carefully. Participants will be provided time to call any family or friends, and given the time they need to make an informed decision about participation. The consent forms will be approved by the IRB, and include a request for participant cell phone number and email address. Cell phone is collected so that participants may be sent study reminders, and email is

requested so that the study personnel might share the intervention resource with participants in the control condition at the end of the study. Participants will also be asked if the study team can record the debriefing session. If so, consent will be obtained.

- IV. Participants will take baseline surveys; this will take approximately 25 minute. Next, participants will receive their experimental materials, which include a Wi-Fi enabled tablet that has been pre-loaded with either intervention or control materials on the browser. Participants will receive verbal and paper-based instructions from the research assistant on how to log into the online, tailored website (intervention condition) or how to access the generic informational website (control condition). Participants will be debriefed, thanked for their time, and scheduled for a slot for their 1-month follow up visit. Participants will receive \$25 for their participation.

One-month follow up:

- Participants will return to the Center for healthful Behavior Change at their 1-month follow up appointment. At this time, participants will be instructed to bring their tablets with them to return the device, and take a follow up survey. The survey will take approximately 25 minutes.
- Participants will be thanked for their time, and scheduled for a slot for their for their 3-month follow up visit. Participants will receive \$50 for their participation.

Three-month follow up:

- Participants will arrive at the CHBC for their 3-month follow up to simply take on last, follow up survey. Participants in the intervention condition will receive \$25 for their participation, debriefed, and released from the study.
- Participants in the control condition will also receive \$25 for their participation, debriefed, and instructed that they will receive access to the intervention resources via email after no later than 3 months.

All outcome measures are located in Table 1.

Table 1 Outcome Measures	Baseline	1 months	3 months
Demographic and Clinical Variables	X		

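### As listed, arrivals are split into intervention and control sessions before consent and the baseline survey, and the supplied text gives neither the timing of randomisation nor how assignment is concealed

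*Combined protocol and SAP*

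**What the plan says.** Section III, Intervention/Control Study, sets out the baseline visit in four numbered steps.

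- Step I gives everyone the same kind of appointment, with no arm named: "All potential participants will be scheduled into an enrollment slot at which time they arrive at the CHBC". It already mentions surveys and instructions.
- Step II divides people by arm: "When participants arrive, they will be invited to go to either the intervention or control enrolment sessions". The stated reason is contamination: "These groups will remain separate so as not to cross-contaminate instructions or materials".
- Step III is consent: "Participants will receive the consent forms, and will be asked to read the documents carefully". No arm-specific form is described.
- Step IV is the survey, "Participants will take baseline surveys; this will take approximately 25 minute", followed by the arm materials: "Next, participants will receive their experimental materials, which include a Wi-Fi enabled tablet".

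On allocation, the Study Design text under Objective 1 says "Participants will be randomized into two groups", with 50 per group. The Study Intervention, Control Condition and data-acquisition paragraphs also mention randomisation, in equally general terms. None gives its timing, who holds the sequence, or how the next assignment is concealed.

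Section II.1 (Recruitment) describes consent at the project office with no split by arm, and rules out any study procedure before written consent.

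**The concern.** Read as a sequence, the steps sort people by arm, then ask for consent, then collect self-reported baseline data. Staff running an arm-labelled session could know the arm throughout. Two things could follow: the people who consent could differ between arms, and the baseline answers could be affected by the setting in which they are given.

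The outcome makes the first more than a formality. The trial measures willingness to join clinical trials and asks about registration with a research registry. Someone who walks away at the consent step is probably less inclined to do either. If one session loses more such people, its consented group looks more willing even when the website does nothing.

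The analysis offers only partial protection. Baseline willingness is collected and could reveal an imbalance. The planned logistic regression on baseline subjective factors could adjust for part of it. Neither can fully repair selection on unmeasured traits, or baseline answers that were themselves affected.

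**Working it through.** **1. Order of events.** Steps I to IV, taken as numbered, give: arrival, arm-specific session (II), consent (III), baseline survey (IV), tablet and arm-specific instructions (IV). No supplied text gives a different order, a time of randomisation or a concealment method. Section II.1 does not explicitly place consent before the split. If assignment counts as a study procedure, its rule on written consent conflicts with the listed order.

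**2. Size.** The plan gives no figure to reproduce and no refusal rate, so this is an illustration.

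Inputs:
- True registration rate *p* = 0.25 in both arms, so no true effect. This is the lower rate in the Section V sample-size calculation; it comes from a pilot on adopting treatment recommendations, so its use here is an assumption.
- 50 consented per arm, the planned group size, with no attrition.
- Share refusing *L* in each session, and the rate *q* at which decliners would have registered: both assumed.

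If a share *L* leaves and those people would have registered at rate *q*, the rate among those who stay is (*p* − *Lq*)/(1 − *L*).

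Worked case, *q* = 0:
- *L* = 10%: 0.25/0.90 = 27.78%
- *L* = 20%: 0.25/0.80 = 31.25%
- False difference: 31.25 − 27.78 = 3.47 points, favouring the session with more refusals.

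Rejection rates come from exact enumeration of two binomials with n = 50 each, two-sided 0.05. With no refusal, or equal refusal at the same *q*, the expected difference is zero. With no refusal the rates are 5.07% (Pearson) and 3.02% (Fisher's exact).

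| Refusal | *q* | Rates among those consenting | False difference (points) | Pearson | Fisher |
|---|---|---|---|---|---|
| 10% v 20% | 0 | 27.78% v 31.25% | 3.47 | 6.65% | 4.29% |
| 10% v 20% | 0.05 | 27.22% v 30.00% | 2.78 | 6.10% | 3.86% |
| 10% v 20% | 0.15 | 26.11% v 27.50% | 1.39 | 5.34% | 3.26% |
| 10% v 20% | 0.20 | 25.56% v 26.25% | 0.69 | 5.14% | 3.10% |
| 0% v 30% | 0 | 25.00% v 35.71% | 10.71 | 21.3% | 15.9% |
| 0% v 30% | 0.05 | 25.00% v 33.57% | 8.57 | 15.5% | 11.2% |
| 0% v 30% | 0.15 | 25.00% v 29.29% | 4.29 | 7.7% | 5.0% |
| 0% v 30% | 0.20 | 25.00% v 27.14% | 2.14 | 5.7% | 3.5% |

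(The first Pearson entry is 6.648% before rounding, hence 6.6% to one decimal.)

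Section V names Fisher's exact test for improvement in health literacy. The planned registration analysis is logistic regression, so neither column is exactly the planned test.

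**The case against.** The strongest reply is that assignment before consent is an inference. Step II does not use the word randomised, and the list may not be strictly chronological, since step I already mentions surveys. The groups are separated to protect instructions and materials, and step IV hands those out only after consent and the survey. The rule in Section II.1 would itself forbid the feared order if assignment is a study procedure. On that reading the fault is in the wording. The flowchart is not shown and the consent pages were removed, so the timing may be stated there.

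The route to bias can also be called thin. Nothing says participants learn their arm before deciding. About 400 potential recruits completed earlier studies and agreed to be contacted again, and telephone callers schedule only interested people. Payment is equal, both arms get a tablet, and controls get the tailored site later. Nothing in the documents predicts that refusal will differ by arm.

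The illustration has limits too. Its refusal rates are invented, and nothing supports 30% v 0%. Some recruits come from the same registry that the registration outcome asks about and may already be registered. The proposed order also presumes individual allocation, while the protocol speaks of a randomised group design.

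Most of this stands as a limit on confidence and size. It does not supply a time of randomisation or a concealment method, and it does not remove the conflict between step II and Section II.1. Staff working from the numbered steps could follow them as written. On the unit of allocation, the Study Design text says that participants are randomised, which supports individual assignment.

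**Conclusion.** The concern holds as a point the protocol should correct, with medium confidence. The listed order puts the split by arm ahead of consent and self-reported baseline data, and the supplied text states neither the timing nor the concealment of randomisation.

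The size and direction of any bias cannot be derived from the documents. Under moderate assumed refusal (10% v 20%) the false difference is at most about 3.5 points, and Fisher's test stays below 5%. Large distortion needs strongly one-sided refusal by people who would rarely register. The case therefore rests on an allocation step that is undefined and, as listed, open to selection, in a trial whose outcome resembles the decision to consent. It does not rest on a prediction of large bias.

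Two assumptions matter: that the session split is the assignment, and that the missing flowchart and consent pages do not settle the order.

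**What to change.** State when randomisation occurs and how the next assignment is concealed from staff who schedule, consent and survey participants. Write the baseline visit in this order:

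1. All arrivals consent and complete the baseline survey under common procedures, with staff unaware of the next assignment.
2. The next concealed assignment is opened.
3. The groups separate for the tablet and arm-specific instructions.

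Contamination is still prevented, because step IV already places the arm materials after the survey. Reconcile steps I to IV with the consent description in Section II.1. Record how many arrivals decline and at which step, and report baseline willingness by arm. If this order is already intended, only the wording of steps I to IV changes.

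The cost is in scheduling; no visit or participant is added. Both arms' materials must be ready at every enrolment slot. Without a second room or staff member, one arm can be instructed after the other, which lengthens the slot for some participants.

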In addition, we will also obtain participants from research match, an online tool used to bridge individuals who are seeking out research studies and researchers who are looking for participants. Participants will be contacted via phone to ascertain their level of interest and eligibility. If participants express interest, they will be invited to come to our project office. Then, a member of the research team will provide detailed information about the study protocol, and read the consent form. Participants will have time to answer questions. No study procedures are conducted without written consent.

Second, in addition to this existing pool of potential participants, others will be recruited who meet the study criteria through community steering committee members, health fairs, and community events. At this time, recruitment will be conducted on site at the requisite health fair or community event. Study fliers will be available for participants who are interested in the study. Participants will have the opportunity to ask the study personnel questions about the study. Those who express interest will be scheduled for an enrollment session to join the study at the Center for Healthful Behavior Change to begin the enrollment process.

For the eligible participants contacted via telephone, the trained research assistant placing these calls will 1) provide detailed information about the study protocol 2) discuss requirements and expectations of participants, and 3) ascertain interest in moving forward with the study. Participants who are interested will be scheduled into an enrollment session. Participants will have time over the phone with the trained research assistant, and also during their assigned enrollment session, to answer questions of the investigative team.

Study Intervention

Participants randomized to the intervention arm will have free access to a password protected interactive culturally and linguistically tailored website via a tablet device. No private identifiable data about you will be collected. Participants will receive a brief 10-

minute tutorial by a trained research assistant on login procedures and use of the website.

Control Condition

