Data acquisition for objective 1: We will use a randomized group design, assessing patient-centered outcomes (health literacy, willingness to participate in a clinical trial, willingness to refer others), contrasting participants who were exposed to health messages via NYU's standard clinical trial website (<http://www.med.nyu.edu/oct/home>) [control arm] and those exposed to the newly created culturally and linguistically tailored website [intervention arm]. They will all complete measures at baseline assessing demographics, general health status (Medical Outcomes Study Short Form), baseline health literacy measures (National Assessment of Adult Literacy), and willingness to participate in a clinical trial ("On a scale from 1 to 5, with 1 being 'not at all willing' and 5 being 'very willing', how willing would you be to participate in a clinical trial in the future?" Response anchors will be; not at all willing, somewhat unwilling, neutral, somewhat willing, and very willing).

At the 1-month debriefing, we will reassess participants' willingness to participate in a clinical trial, and ask whether or not they opted to register with ResearchMatch; an online volunteer clinical research registry. These data will help establish a model for future translational and dissemination research. At the end of the 2-year project, we expect to have developed a culturally-tailored clinical trial literacy website that could be widely accessed. There are over 31,000 racial/ethnic minority barbershops, beauty salons, and faith-based organizations across the United States that could use this non-traditional model promoting participation in clinical trials. The long-term goal is to use this infrastructure for dissemination of evidence-based clinical trial health literacy and participation at the community level.

Schedule of Events

The primary aim of this study is to compare the tailored materials to control information only materials that are not tailored to the population being studied. However, before the Intervention/Control study, all messages and online resources will be assessed using cognitive heuristic testing to ensure the website is user friendly and culturally and linguistically tailored to the population. Heuristic testing to ensure cultural and linguistic appropriateness of the resource will be conducted, followed by the Intervention/Control study.

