Medical Outcomes Study Short Form 36	X		
Internet Self-efficacy Scale	X	X	X
Clinical Trials Literacy	X	X	X

Message Effectiveness Scale		X	X
Clinical Vignette			X

IV. DATA ANALYSIS AND DATA MONITORING

Throughout the study, [name] will oversee data entry and verification, ensure adherence to coding, clean and edit protocols. Data will be maintained on a password-protected PC with backup copies kept on external disks in a secured location.

Participant-identifying information will be kept in a locked file cabinet with only numerical identifiers in computer files.

Hypothesis 1: Participants exposed to tailored messages about clinical trial literacy will exhibit greater likelihood in participating in clinical trials than those exposed to NYU's standard website. Secondly, we expect them to show greater likelihood to refer others to clinical trials as well.

Analysis: While the primary goal of the study is to develop and test effectiveness of tailored messages to overcome identified barriers to participating in clinical trials, the secondary goal is to examine factors likely to facilitate adoption of such messages. All participants in the intervention arm will have been exposed to all tailored web-based messages. To compare participants who exhibited improvement in health literacy and those who did not 2-months post-enrollment, t-tests and chi-squared tests will be used. Baseline subjective factors will be entered in a logistic regression model in order to determine which factors are associated with higher likelihood of (a) registering to participate in clinical trials, contrasting individuals in the two study arms and (b) referring others to participate as well. Multivariate analysis of covariance will be used to assess effects of messages on the secondary outcome: health literacy scores; effects of sociodemographic confounders will be adjusted.

Hypothesis 2: Greater likelihood of participating in clinical trials will be mediated by greater health literacy and/or self-efficacy independent of other individual-level factors (medical, knowledge, attitude/beliefs, and intrinsic motivation) and contextual-level factors (social support and socio-economic position).

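### Table 1 has no row for willingness, ResearchMatch registration or referral; referral has no item or named visit, and registration has no baseline status although some participants come from ResearchMatch

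*Combined protocol and SAP*

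**What the plan says.** Under Intervention/Control Study, the protocol closes its description of the three visits with "All outcome measures are located in Table 1". The table header is "Table 1 Outcome Measures Baseline 1 months 3 months". Its rows are demographic and clinical variables, the SF-36, Internet self-efficacy, literacy ("Clinical Trials Literacy X X X"), message effectiveness (1 and 3 months) and a vignette ("Clinical Vignette X", at 3 months only).

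Section IV states Hypothesis 1 as greater likelihood of participating, and then adds "Secondly, we expect them to show greater likelihood to refer others to clinical trials as well". The analysis fits a logistic regression for (a) registering for trials and "b) referring others to participate as well".

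Data acquisition for objective 1 (Section III) gives the wording of a 1-to-5 willingness item at baseline. At 1 month it repeats willingness and asks whether the participant chose to register with ResearchMatch. For literacy it names "baseline health literacy measures (National Assessment of Adult Literacy"), an instrument that has no row in Table 1. On recruitment, Section II.1 says "we will also obtain participants from research match".

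**The concern.** A schedule that declares itself complete is what staff build the survey from. If it omits outcomes that the analysis section models, they may be collected inconsistently or not at all, and an answer not taken before exposure cannot be recovered reliably later.

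Two outcomes are exposed. Referral has a planned analysis but no described measurement. Registration is measured once, after exposure, in a sample recruited partly from the same registry. Without baseline status, the analysis cannot separate someone who registered because of the website from someone who was already on the registry.

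**Working it through.** **Step 1. Set each outcome against the table and the text.**

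| Outcome | Row in Table 1 | Visit named in the text | Item given |
|---|---|---|---|
| Willingness to participate | none | baseline, 1 month (Data acquisition) | yes, 1-to-5 scale |
| ResearchMatch registration | none | 1 month only (Data acquisition) | yes/no question described |
| Referral of others | none | none; Study Design says only before and after exposure | none |
| Literacy | Clinical Trials Literacy, all three visits | adult literacy measure at baseline (Data acquisition) | instrument names only |

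The completeness statement therefore fails for three outcomes. For two of them the text supplies visits. For referral it supplies neither an item nor a named visit.

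The referral construct is also unsettled. Study Design and Data acquisition speak of likelihood of, or willingness for, referral, which is an intention. The logistic regression in Section IV is worded as referring, which is a behaviour.

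**Step 2. Effect of missing baseline registration.** Inputs:
- Rates without the intervention and with it: 25% and 45%, from Section V. These are adoption rates for treatment recommendations in an earlier pilot, used here because the plan powers on them.
- Share already registered, s: not in the documents. Assumed to be 10%, 20% or 30%, and equal in both arms.

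If those already registered answer yes, the observed rate is s + (1 − s) × p, so the difference is (1 − s) × 20 points.

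| s | Control | Intervention | Difference |
|---|---|---|---|
| 0% | 25% | 45% | 20 points |
| 10% | 0.10 + 0.90 × 0.25 = 32.5% | 0.10 + 0.90 × 0.45 = 50.5% | 18 points |
| 20% | 0.20 + 0.80 × 0.25 = 40% | 0.20 + 0.80 × 0.45 = 56% | 16 points |
| 30% | 0.30 + 0.70 × 0.25 = 47.5% | 0.30 + 0.70 × 0.45 = 61.5% | 14 points |

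If they answer no instead, the rate is (1 − s) × p and the difference is again (1 − s) × 20 points. At 20%, for example, it is 20% versus 36%, or 16 points. The shrinkage comes from keeping people who cannot newly register in the denominator. The answer they give decides only whether they are also counted as successes.

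**Step 3. Does excluding them cost more than it gains?** Compare the difference divided by its standard error, √[(p₁(1 − p₁) + p₂(1 − p₂))/n], with 50 per arm enrolled and no loss to follow-up.

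| s | All included, yes answers, n = 50 | Not registered at baseline only |
|---|---|---|
| 10% | 0.18/√(0.46935/50) = 1.86 | 0.20/√(0.435/45) = 2.03 |
| 20% | 0.16/√(0.4864/50) = 1.62 | 0.20/√(0.435/40) = 1.92 |
| 30% | 0.14/√(0.48615/50) = 1.42 | 0.20/√(0.435/35) = 1.79 |

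The smaller denominator gives the stronger comparison at each of these shares.

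**The case against.** Much can be said for the plan. Willingness and registration have collection points in the text, so the gap for them is one of cross-reference. Referral is said to be assessed before and after exposure, and the consent section tells participants that the study will ask about it. The surveys are not reproduced, and the message effectiveness scale and the vignette are not described, so either might hold a referral question. This stands as a reason not to say that referral will go uncollected. It does not close the gap: neither instrument is scheduled at baseline, so neither could supply the measurement before exposure.

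The registration question asks about a choice to register, and participants may understand it as a choice made since enrolment. So prior registrants could, not would, be counted as successes. The dilution in step 2 remains in either case.

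Three stronger readings are tempting and not supported:
- *Table 1 omits every outcome analysed under Hypothesis 1.* Literacy is the named secondary outcome there, and it has a row.
- *Half of Hypothesis 1 cannot be tested.* Referral is an added second part in Section IV and is absent from Hypothesis 1 as stated with the objectives. The participation part has visits.
- *Literacy will be measured on one instrument before exposure and another after.* Table 1 schedules Clinical Trials Literacy at all three visits. What is unclear is only which instrument the analysis means by health literacy.

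**Conclusion.** The point holds in this form. Table 1 contradicts its own completeness statement for willingness, registration and referral. Referral, a modelled outcome, lacks an item and a named visit. Registration lacks a baseline status that the recruitment route makes necessary.

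The first two conclusions follow from the text alone. The size of the third rests on assumptions: that people recruited through ResearchMatch are already registered on it, that their share is the same in both arms and they answer alike, and that the pilot rates carry over to registration. On that basis the 20-point difference falls to between 18 and 14 points for shares of 10% to 30%. The actual share is unknown, and the loss is proportional to it. The literacy ambiguity is minor and needs one clarifying sentence.

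**What to change.** 1. Ask ResearchMatch registration in the baseline survey, before the tablet is handed out. Define the outcome as new registration among participants not registered at baseline.
2. Add a referral item at baseline and at the 1-month visit, and at 3 months if that visit is to be analysed. State whether it measures intention or actual referral, and how it is coded for the logistic regression.
3. Add rows for willingness, registration and referral to Table 1, matching the visits in the text.
4. State whether health literacy in the Section IV analyses means Clinical Trials Literacy, the only literacy measure that Table 1 schedules before and after exposure, or the National Assessment of Adult Literacy.

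The cost is a table edit, a few questions at visits already planned, and a smaller denominator for registration: 45, 40 or 35 of 50 per arm at the assumed shares.
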